**Table 2. Study Activities (Period 1) (Continued)**

Activity	Screening D-35 to D-1	BL	Wk 2	Wk 4	Wk 8	Wk 12	Wk 14	Wk 18	Wk 22	Wk 26	Wk 30	Wk 36	Wk 42	Wk 48/ PD a	30- Day F/U Visit/ Call c	70- Day F/U Call c
		D1 b	D15	D29	D57	D85	D99	D127	D155	D183	D211	D253	D295	D337		
Patient questionnaires h FACIT-F EQ-5D-5L SF-36 RA-WIS		X				X				X				X		
Latent TB risk assessment form i	X													X i		
Central lab QuantiferON-TB Gold test l (and/or local PPD skin test)	X													X		
Chest x-ray j	X													X		
12-lead ECG k	X													X l		
X-rays (bilateral hands/feet)	X m						X n			X n				X n		
Height (screening only) and weight	X	X	X	X	X	X	X	X	X	X	X	X	X	X	X	
Vital signs o	X	X	X	X	X	X	X	X	X	X	X	X	X	X	X	
Physical exam p	X	X												X		
Physician Global Assessment (PhGA)		X	X	X	X	X	X	X	X	X	X	X	X	X		

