**Table 2. Study Activities (Period 1) (Continued)**

- a. If a subject is prematurely discontinued from study drug, the procedures outlined for the Premature Discontinuation visit (PD visit) should be completed as soon as possible, preferably within 2 weeks of study drug discontinuation.
- b. The Baseline visit procedures will serve as the reference for all subsequent visits with the exception of the ECG and x-rays of hands and feet, which will be obtained at Screening only and used as the baseline reference (see also footnote m regarding x-rays of the hands and feet at Screening).
- c. This visit is 30 days after last dose of study drug for those subjects who complete Period 1 and do NOT enter Period 2. A 30-day follow-up phone call may be allowed for subjects who have completed the PD visit to determine the status of any ongoing AEs/SAEs or the occurrence of any new AEs/SAEs. The 70-day follow-up call to take place 70 days after last dose of subcutaneous study drug for those subjects who complete Period 1 and do NOT enter Period 2 and for those who prematurely discontinue the study (withdrawal of informed consent). The 70 day follow-up phone call will not be required for any subject that initiates commercial adalimumab.
- d. Informed consent should be obtained at Screening prior to performing any study related procedures.
- e. Note herpes zoster and hepatitis B vaccination status in medical history.
- f. Collect serious adverse events and protocol-related nonserious AEs that occur after a subject signs the informed consent, prior to the first dose of study drug.
- g. At Week 48 (after Week 48 assessments have been performed), per Investigator judgment, may add or change csDMARDs (concomitant use of up to 2 csDMARDs, except the combination of MTX and leflunomide, or increasing csDMARD dose).
- h. Prior to other procedures.
- i. Complete the latent TB risk assessment form annually. Refer to Section 5.3.1.1. Study Procedures TB Testing for specific requirements for TB testing and TB Prophylaxis.

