**Table 4. Study Activities (Period 2) (Continued)**

- c. Prior to other procedures.
- d. TB testing should be performed every 48 weeks after Week 96 in subjects with previous negative QuantiFERON-TB Gold and/or PPD tests. Subjects with new evidence of latent TB should initiate prophylactic treatment immediately per local guidelines. Refer to Section 5.3.1.1, Study Procedures, TB Testing for specific requirements for TB testing and TB Prophylaxis. Study drug(s) should not be withheld at the time of the first positive TB test.
- e. Obtain chest x-ray every 48 weeks after Week 96 for subjects with newly identified TB risk factors based on the TB risk assessment form, or for subjects living in areas endemic for TB, or for subjects with a newly positive QuantiFERON-TB Gold test (and/or PPD skin test) after baseline.
- f. ECGs will be performed every 48 weeks after Week 48. An ECG may be performed at any visit if deemed necessary by the Investigator.
- g. X-rays of hands and feet must be performed at Week 96 and every 96 weeks thereafter. Subjects who prematurely discontinue from the study will not need an x-ray of hands and feet if the previous x-ray was performed within the previous [redacted] weeks.
- h. Blood pressure, pulse rate, body temperature, and respiratory rate should be performed before blood draws are performed.
- i. A full physical exam is required every 24 weeks after Week 96. A symptom-directed physical exam may be performed when necessary.
- j. For women of childbearing potential, a urine pregnancy test will be performed at all visits and monthly at home between scheduled study visits. The results of the monthly at home tests will be communicated to the site. If a urine pregnancy test is positive, the subject must stop dosing, come in to the clinic and have blood drawn for a serum pregnancy test that will be analyzed at the central laboratory. Pregnant subjects must discontinue from study drug treatment. Refer to Section 5.3.1.1 Study Procedures Pregnancy Test for additional details.
- k. Starting at Week 48, for women of childbearing potential, in-home urine pregnancy tests will be performed monthly.
- l. hsCRP results will remain blinded to Sponsor, Investigator and study site personnel, and the subject for all visits until the last subject reaches the end of Period 1.

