### **TB Testing/TB Prophylaxis**

The TB screening tests provide diagnostic test results to be interpreted in the context of the subject's epidemiology, history, exam findings, etc., and it is the responsibility of the Investigator to determine if a subject has previous, active, or latent TB. Expert consultation for the evaluation and/or management of TB may be considered per Investigator discretion.

At screening, all subjects will be assessed for evidence of increased risk for TB by a risk assessment form ([Appendix F](#)) and tested for TB infection by QuantiFERON-TB Gold test. The PPD Skin Test should be utilized only when a QuantiFERON-TB Gold Test is not possible for any reason (unless both tests are required per local guidelines). The site staff will complete the TB risk assessment form and enter the data into an appropriate eCRF. The TB risk assessment form will be completed annually for all subjects, regardless of TB test results.

If a subject had a negative PPD test within 90 days prior to Screening and a QuantiFERON-TB Gold test cannot be performed by Central Lab at Screening and source documentation is available, TB testing by PPD Skin Test does not need to be repeated, provided nothing has changed in the subject's medical history to warrant a repeat test. These cases may be discussed with the AbbVie TA MD. The results of the TB test(s) will be retained at the site as the original source documentation.

Subjects with a negative TB test and chest x-ray (CXR) not suggestive of active TB or prior TB exposure may be enrolled.

Subjects with a positive TB test must be assessed for evidence of active TB versus latent TB, including signs and symptoms and CXR. Subjects with no signs or symptoms and a CXR not suggestive of active TB may be enrolled after initiation of TB prophylaxis (see below).

Subjects with evidence of active TB must not be enrolled.

For subjects with a negative TB test result at Screening or the most recent evaluation, an annual TB follow-up test will be performed. If an annual TB test is newly positive (seroconversion), a chest x-ray (CXR) needs to be performed as soon as possible to aid in distinguishing active versus latent TB. Any positive TB screen after the patient has started the study, should be reported as an AE of latent TB or active TB (as applicable).

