If the subject is experiencing signs or symptoms suspicious for TB or something has changed in the subject's medical history to warrant a repeat test before the next scheduled annual TB re-test, the case (including the TB test results) must be discussed with the AbbVie TA MD.

TB test:

- Subjects with documentation of prior positive result of QuantiFERON-TB Gold Test (or equivalent) and/or PPD are not required to repeat either test at Screening or during the study and should be considered positive.
- For regions that require both PPD and QuantiFERON-TB Gold testing, both will be performed. If either PPD or QuantiFERON-TB Gold are positive, the TB test is considered positive.
- The PPD Skin Test (also known as a TB Skin Test or Mantoux Test) should be utilized only when a QuantiFERON-TB Gold Test is not possible for any reason (unless both tests are required per local guidelines).

- If only a PPD is placed at screening, then the TB test to be used for the remainder of the study for that subject is the PPD. Similarly, if a subject enters the study with a QuantiFERON-TB Gold test (or equivalent) alone, then the subject should have their annual TB test performed with a QuantiFERON-TB Gold test.
- If the QuantiFERON-TB Gold Test is NOT possible (or if both the QuantiFERON-TB Gold Test and the PPD are required per local guidelines) the PPD will be performed. The PPD should be read by a licensed healthcare professional between 48 and 72 hours after administration. A subject who does not return within 72 hours will need to be rescheduled for another skin test. The reaction will be measured in millimeters (mm) of induration and induration  $\geq 5$  mm is considered a positive reaction. The absence of induration will be recorded as "0 mm" not "negative." Subjects who have an ulcerating reaction to the PPD in the past should not be re-exposed and the PPD should be considered positive.
- If the QuantiFERON-TB Gold test is indeterminate, then the investigator should perform a local QuantiFERON-TB Gold test (or through the central laboratory if not locally available) to rule out a positive test result. If testing remains indeterminate or is positive, then the subject is considered to be positive for the purpose of this study. If the testing result is negative, then the patient is considered to be negative.

For sites participating from the Czech Republic, the following local requirements will also be applicable:

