10.1.3 Long-Term Safety Analysis

Long-term safety analyses include reporting of AE rate adjusted by cumulative exposure, mean change from baseline in laboratory parameters and vital sign variables, and frequency of potentially clinically significant laboratory and vital signs values.

The treatment-emergent adverse event (TEAE) rate per 100 patient-years of exposure will be presented by actual treatment received (i.e., exposed to) at the time of AE (treatment exposure for subjects switching treatments is described in Section 8.1). Listing of subjects with TEAEs by SOC and PT will be provided. Frequency tables and listings of subjects meeting criteria for potentially clinically significant vital sign values and for potentially clinically significant laboratory values will be provided by actual treatment received at the time of event.

For long-term analysis of TEAEs and potentially clinically significant laboratory or vital signs values, two sets of summaries will be provided, namely "summary based on all study drug exposure" and "summary based on long-term study drug."

Summary based on all study drug exposure:

This summary will take into account safety data under the exposure of each study drug for each subject, i.e., an all-inclusive summary. The summary will be grouped by study drug as follows (and as illustrated in the figure below):

[figure not shown]
1. Placebo

2. Any ADA 40 mg EOW

This includes ADA exposure from subjects starting on ADA 40 mg EOW and subjects rescued from Upadacitinib 15 mg QD to ADA 40 mg EOW

3. Any Upadacitinib 15 mg QD

This includes Upadacitinib 15 mg QD exposure from subjects starting on Upadacitinib 15 mg QD, subjects rescued/switched from placebo to Upadacitinib 15 mg QD, and subjects rescued from ADA 40 mg EOW to Upadacitinib 15 mg QD

UPA = upadacitinib; ADA = adalimumab; PBO = placebo; WK = week; trt = treatment

* Treatment switching may occur at Week 14, 18, 22 or 26. Treatment switching in the graph is positioned between Week 14 and Week 26 for illustration purposes.

1. Belongs to group 1: Placebo.
2. Belongs to group 2: Any ADA 40 mg EOW.
3. Belongs to group 3: Any Upadacitinib 15 mg QD.

Summary based on long-term study drug:

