10.2.2.1 Overview of Adverse Events Rates per 100 Patient-Years of Study Drug Exposure

An overview of AEs per 100 patient-years of study exposure will be presented by treatment group and overall for the following AE categories.

- All TEAEs
- Treatment-emergent serious adverse events (SAEs)
- Treatment-emergent severe adverse events
- TEAEs reasonably possibly related to study drug

- TEAEs of special interest
- TEAEs leading to discontinuation of study drug
- TEAE leading to death

For this calculation, one year will be considered to be 365.25 days. For each treatment group, the numerator of the overall rate will be the total number of TEAEs reported for the event; that is, a subject can contribute more than one event to the numerator. For each treatment group, the denominator of the rates will be the total number of days exposed to study drug summed across all treated subjects divided by 365.25. Please refer to Section 6.0 for the calculation of study drug exposure. The AE rate per 100 patient-years of exposure will be calculated as $(\text{[numerator/denominator]}) \times 100$. The number of AEs reported (numerator), the total number of years of study drug exposure (denominator), and the AE rate per 100 patient-years will be presented for each treatment group and overall.

Additional AEs may be considered for tabulation/summary based on recommendations from Clinical and Safety as deemed appropriate.

For TEAEs of special interest, the point estimate and 95% CI (using normal approximation) will be provided for the treatment difference in AE rates per 100 patient-years.

10.2.2.2 Adverse Events Rates per 100 Patient-Years of Study Drug Exposure by SOC and PT

For each treatment group, the TEAE rate per 100 patient-years of exposure will be calculated overall, for each SOC and each PT, for each of the following events:

- All TEAEs
- Treatment-emergent serious adverse events (SAEs)
- Treatment-emergent severe adverse events
- TEAEs reasonably possibly related to study drug
- TEAEs leading to discontinuation of study drug
- TEAE leading to death

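### In the long-term all-exposure safety summary, test-detected latent TB is not ascertained alike across groups: placebo ends before the first routine test, and Week 48 positives count against the drug then being taken

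*SAP*

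**What the plan says.** **Reporting.** Protocol 5.3.1.1 (TB Testing/TB Prophylaxis) states: "Any positive TB screen after the patient has started the study, should be reported as an AE of latent TB or active TB". An asymptomatic conversion therefore becomes an adverse event once a test finds it.

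**Test calendar.** The same section says that for subjects with a negative result "an annual TB follow-up test will be performed". In Protocol Table 2 the TB test row (central QuantiFERON "and/or local PPD skin test") is marked only at Screening and in the Week 48/PD column. For Period 2, Table 4 marks Week 96 and every 48 weeks, and its note d reads: "TB testing should be performed every 48 weeks after Week 96 in subjects with previous negative QuantiFERON-TB Gold and/or PPD tests". Two other routes to a test exist. Table 2 note a says "If a subject is prematurely discontinued from study drug, the procedures outlined for the Premature Discontinuation visit (PD visit) should be completed". Protocol 5.3.1.1 also foresees a case where "something has changed in the subject's medical history to warrant a repeat test before the next scheduled annual TB re-test".

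**End of placebo.** Under Protocol 5.2.3.3, placebo subjects are rescued to upadacitinib at Week 14, 18 or 22, and all who remain are switched at Week 26.

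**Attribution.** Under SAP 10.1.3 the long-term event rate "will be presented by actual treatment received (i.e., exposed to) at the time of AE". The all-exposure summary has three groups: placebo, any adalimumab (ADA) and any upadacitinib. SAP 8.1 starts new-drug exposure on the day the new drug is initiated.

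**Comparison.** For events of special interest, SAP 10.2.2.1 says that a point estimate and 95% CI "will be provided for the treatment difference in AE rates per 100 patient-years". Tuberculosis is on that list (Protocol 6.1.1.3; SAP Table 10). Neither document schedules a TB test at the switch or gives a rule for events found only by testing.

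**The concern.** An event that exists only once a test is done can be counted only where tests are done. Switching divides a subject's exposure between two drugs, but the single Week 48 test assigns every conversion since Screening to the second drug. The denominator is split and the numerator is not.

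The placebo group thus has person-time but almost no chance of a test-detected event. The groups that receive switched subjects have events whose person-time lies partly elsewhere. Infection is a safety topic of interest for an immunomodulator, and a rate pattern produced by the test calendar could be read as a drug effect, or could mask one.

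**Working it through.** The plan states no figure for this, so there is nothing to reproduce. The check has three steps.

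**1. Can a Week 48 test give a placebo event?** Protocol Table 2 puts Week 26 at Day 183 and Week 48 at Day 337. The gap is 337 − 183 = 154 days. SAP 10.2 counts an event as treatment-emergent for placebo up to 30 days after the last dose. So no Week 48 test can yield a placebo event. Only a PD-visit or unscheduled test can.

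**2. Inflation that does not depend on the conversion rate.** Assume the same constant conversion rate on every treatment, detection only at scheduled tests, and event onset at the test date.

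- Subject switched from placebo at week s: the Week 48 test captures 48 weeks of conversions, set against 48 − s weeks on upadacitinib. Inflation = 48/(48 − s).
  - s = 14: 48/34 = 1.41
  - s = 18: 48/30 = 1.60
  - s = 22: 48/26 = 1.85
  - s = 26: 48/22 = 2.18
- Mixed switching, where the shares are assumptions: 30% at Week 14 and the rest at Week 26 gives 48/(0.3 × 34 + 0.7 × 22) = 48/25.6 = 1.88. With 50% at Week 14 it is 48/28 = 1.71.
- Pooled any-upadacitinib in Period 1, with 600 randomised to each of upadacitinib and placebo, all placebo switching at Week 26, no dropout and no ADA/upadacitinib switching: (48 + 48)/(48 + 22) = 96/70 = 1.37.
- Same pool through a Week 288 test: (2 × 288)/(288 + 262) = 576/550 = 1.05.

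The same formula applies to a subject switched between ADA and upadacitinib, in either direction. The second drug gains the first drug's conversions, and the first drug keeps the person-time without them.

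**3. Illustrative counts.** The conversion rate c is an assumption, with range 0.5 to 3 per 100 patient-years (PY). Placebo N = 600. The 10% dropout figure is the one in Protocol 8.2. I spread it evenly over Weeks 0–26 (mean 13 weeks), with a PD test for each dropout and all others switching at Week 26. One year = 365.25/7 = 52.18 weeks.

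- Placebo exposure: (60 × 13 + 540 × 26)/52.18 = 284 PY.
- Placebo-attributed detections at c = 1: (60 × 13/52.18) × 0.01 = 0.15, or about 0.05 per 100 PY.
- Placebo-to-upadacitinib exposure in Period 1: 540 × 22/52.18 = 228 PY.
- Week 48 detections in that group at c = 1: (540 × 48/52.18) × 0.01 = 4.97, or 2.18 per 100 PY.
- Of these, acquired on placebo: (540 × 26/52.18) × 0.01 = 2.69.

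| Assumed c (per 100 PY) | Placebo-attributed | Acquired on placebo, counted on upadacitinib |
|---|---|---|
| 0.5 | 0.07 | 1.35 |
| 1 | 0.15 | 2.69 |
| 3 | 0.45 | 8.07 |

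With no dropout, scheduled tests give zero placebo detections over 600 × 26/52.18 = 299 PY.

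**The case against.** The case against narrows the point in several ways.

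- **Other summaries are sound.** SAP 10.1.1 and 10.1.2 compare the arms up to Week 14, and up to Week 26 censored at switching. No arm has a routine test before Week 48, so ascertainment there is low but equal by schedule. The long-term-study-drug summary in SAP 10.1.3 has no placebo group and keeps switched and non-switched subjects apart. Its two non-switching groups share one calendar and carry nothing over from another study drug. This stands. The carry-over does remain in its three switched groups.
- **Special-interest status is uncertain.** SAP Table 10 defines tuberculosis by a company query whose terms are not listed. A reader might infer that the planned TB rate difference is biased; the documents support that only if the query includes latent TB. The overall, SOC and PT rates are affected either way, but SAP 10.2.2.2 plans no differences or intervals for them.
- **The direction is not fixed.** A reader might infer that upadacitinib must show an excess. Subjects moved from upadacitinib to ADA take conversions away from upadacitinib and leave their exposure behind. SAP 9.3.1 also notes that not all subjects can have reached Week 48 by the Week 26 lock. At that lock much upadacitinib exposure is untested, and its rate could fall below the true one.
- **Placebo is not forced to zero.** PD-visit and unscheduled tests remain possible.
- **Onset date.** Neither document fixes the onset date of a positive screen. Taking the test date is an assumption.

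The SAP does allow additional tabulations at discretion. That permission does not prespecify how test-detected events are to be handled.

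**Conclusion.** The point holds for the long-term all-exposure summary. Test-detected latent TB is close to unobservable on placebo there, and Week 48 positives in switched subjects count against the later drug.

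Under equal true rates and detection only at scheduled tests, the Period 1 inflation is 1.41- to 2.18-fold in placebo-to-upadacitinib subjects. It is up to about 1.37-fold in the pooled upadacitinib group, under the simplifications stated above. The pooled figure falls to about 1.05 by Week 288, but later follow-up cannot fill the placebo group. All of these figures take event onset as the test date.

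The effect on the special-interest rate difference depends on a query that is not shown. The documents do not support a claim that upadacitinib will necessarily show an excess, or that the Week 14 and Week 26 comparisons are biased. A correction before the long-term tables are produced is worthwhile because it is cheap and removes the artefact.

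**What to change.** In SAP 10.2.1.6 and 10.2.2:

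- Keep tuberculosis as an event of special interest, but present active TB and test-detected latent TB separately. Redefining the protocol-listed category as active TB alone is not needed.
- Give exposure-adjusted rates and rate differences for active TB.
- Report latent TB as converters over subjects tested at each scheduled test (Week 48/PD, Week 96 and so on), by the five treatment sequences already listed at the end of SAP 10.1.3, with no placebo rate contrast. Those sequences have no placebo-only row, so say where subjects who stop on placebo before any switch are shown.
- Footnote the all-exposure SOC and PT table to say that latent TB is found mainly at scheduled tests, the first of them after placebo has ended.

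The cost is SAP wording and one small extra table. No visit, test or treatment rule changes.

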## **5.4 Removal of Subjects from Therapy or Assessment**

### **5.4.1 Discontinuation of Individual Subjects**

Subjects can request to be discontinued from participating in the study at any time for any reason, including but not limited to disease progression or lack of response to treatment. The Investigator may discontinue any subject's participation for any reason, including an AE, safety concerns, lack of efficacy, or failure to comply with the protocol. See Section 6.1.7 for toxicity management criteria.

Subjects will have study drug treatment discontinued immediately if any of the following occur:

- Clinically significant abnormal laboratory results or AEs, which rule out continuation of the study drug, as determined by the Investigator or the AbbVie Therapeutic Area Medical Director.
- Serious infections (e.g., sepsis) which cannot be adequately controlled within 2 weeks by anti-infective treatment or would put the subject at risk for continued participation in the trial as determined by the Investigator.
- The Investigator believes it is in the best interest of the subject.
- The subject requests withdrawal from the study.
- Inclusion or exclusion criteria violation was noted after the subject started study drug, when continuation of the study drug would place the subject at risk as determined by the AbbVie Therapeutic Area Medical Director.
- Introduction of prohibited medications or dosages when continuation of the study drug would place the subject at risk, as determined by the AbbVie Therapeutic Area Medical Director.
- Subject is non-compliant with TB prophylaxis (if applicable) or develops active TB at any time during the study.
- The subject becomes pregnant while on study drug.
- Malignancy, except for localized NMSC or carcinoma in situ of the cervix.
- Subject is diagnosed with lupus-like syndrome, multiple sclerosis, or demyelinating disease.

- Subject is significantly non-compliant with study procedures which would put the subject at risk for continued participation as determined by the Investigator.
- Subject develops a gastrointestinal perforation.
- Subjects with disease progression or not responding to treatment are to be withdrawn from the trial based on investigator's discretion.

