Period 1 will begin at the Baseline Visit (Day 1) and will end at the Week 48 Visit. At the Baseline Visit, subjects who meet all the inclusion criteria and none of the exclusion criteria will be enrolled into the study and randomized to double-blind treatment. During this period of the study, subjects will visit the study site at Weeks 2, 4, 8, 12, 14, 18, 22, 26, 30, 36, 42, and 48. A ± 3 day window is permitted around scheduled study visits until Week 30 and ± 7 days for the remainder of the period. The last dose of oral study drug in Period 1 is taken the day prior to the Week 48 visit. Subjects who complete Period 1, but decide not to continue in Period 2 should complete a 30 day follow-up visit after the last dose of study drug.

Period 2 (Long-Term Extension Period [up to 5 Years])

Period 2 will begin at the Week 48 visit after all assessments have been completed. During Period 2, subjects will have a study visit at Weeks 60, 72, 84, 96, and every 12 weeks thereafter until completion of the study. A ± 7 day window is permitted around scheduled study visits. Starting at Week 48, subjects who failed to show at least 20% improvement in TJC and SJC compared to baseline at 2 consecutive visits will be discontinued from study drug treatment.

Discontinuation of Study Drug and Continuation of Study Participation (Period 1 and Period 2)

Subjects may discontinue study drug treatment, but choose to continue to participate in the study. Subjects who prematurely discontinue study drug should complete a Premature Discontinuation Visit (PD visit) as soon as possible, preferably within 2 weeks. Subjects should follow the regular visit schedule specified in the protocol, and adhere to all study procedures except for dispensing study drug, PK sample collection, and blood sample collection for optional exploratory research and validation studies. In addition, all future rescue and efficacy-driven discontinuation criteria no longer apply for these subjects; this includes 20% TJC/SJC calculations at Weeks 14 – 22, and Week 48 and thereafter, as well as CDAI calculation at Week 26, if applicable. If at any point a subject no longer wants to provide assessments (withdrawal of informed consent) following discontinuation of study drug, a second PD visit is not required.

Premature Discontinuation of Study (Withdrawal of Informed Consent) (Period 1 and Period 2)

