"Summary based on long-term study drug" considers safety data from the study drug for which a subject will remain on long-term for the rest of the study. For subjects who did not switch treatment during the study, all safety data under the original study drug will be summarized. For subjects who switched treatment during the study, safety data under the study drug that they switched to (i.e., the second study drug) will be summarized; in this case, safety data from the first study drug is only short-term and therefore will not be included in this summary. The treatment groups for this summary are as follows (and as illustrated in the figure below):

1. Upadacitinib 15 mg QD, switched from Placebo

This includes Upadacitinib 15 mg QD exposure from subjects who switched from placebo to Upadacitinib 15 mg QD (either due to rescue treatment switch or systematic switch at Week 26)

2. Upadacitinib 15 mg QD, no treatment switching

This includes Upadacitinib 15 mg QD exposure from subjects starting on Upadacitinib 15 mg QD and who did not switch study treatment due to rescue

3. ADA 40 mg EOW, no treatment switching

[figure not shown]
This includes ADA 40 mg EOW exposure from subjects starting on ADA 40 mg EOW and who did not switch study treatment due to rescue

4. Upadacitinib 15 mg QD, switched from ADA

This includes Upadacitinib 15 mg QD exposure from subjects who switched from ADA 40 mg EOW to Upadacitinib 15 mg QD

5. ADA 40 mg EOW, switched from Upadacitinib

This includes ADA 40 mg EOW exposure from subjects who switched from Upadacitinib 15 mg QD to ADA 40 mg EOW

UPA = upadacitinib; ADA = adalimumab; PBO = placebo; WK = week; trt = treatment

* Treatment switching may occur at Week 14, 18, 22 or 26. Treatment switching in the graph is positioned between Week 14 and Week 26 for illustration purposes.

1. Belongs to group 1: Upadacitinib 15 mg QD, switched from Placebo.
2. Belongs to group 2: Upadacitinib 15 mg QD, no treatment switching.
3. Belongs to group 3: ADA 40 mg EOW, no treatment switching.
4. Belongs to group 4: Upadacitinib 15 mg QD, switched from ADA.
5. Belongs to group 5: ADA 40 mg EOW, switched from Upadacitinib.

In addition to the analyses described above, mean changes from baseline in all continuous laboratory parameters and vital signs variables at each visit will be summarized by "as treated" treatment group sequences defined as follows:

1. Placebo → Upadacitinib 15 mg QD
2. ADA 40 mg EOW
3. ADA 40 mg EOW → Upadacitinib 15 mg QD

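### In the SAP 10.1.3 summary based on long-term study drug, the two no-switch groups' rates of death, AE discontinuation and drug-stopping AESI are inflated by the way the groups are defined

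*SAP*

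**What the plan says.** SAP 10.1.3 defines five groups for the summary by long-term study drug. Groups 2 (upadacitinib) and 3 (adalimumab) are the no-switch groups. Group 2 takes "exposure from subjects starting on Upadacitinib 15 mg QD and who did not switch study treatment due to rescue", and group 3 is worded the same way. The section states the rule for these subjects: "For subjects who did not switch treatment during the study, all safety data under the original study drug will be summarized". For switchers only the second drug counts: "safety data from the first study drug is only short-term and therefore will not be included in this summary". Groups 1, 4 and 5 hold the second-drug data of subjects switched from placebo, adalimumab and upadacitinib.

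The figure note in the same section gives the timing: "Treatment switching may occur at Week 14, 18, 22 or 26". SAP 4.2 says that once study drug is stopped, "all future rescue and efficacy-driven discontinuation criteria no longer apply for these subjects".

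SAP 10.2.2 applies these groups to adverse event rates. Within each group, "the denominator of the rates will be the total number of days exposed to study drug summed across all treated subjects divided by 365.25" (SAP 10.2.2.1). The categories include AEs leading to death, AEs leading to study drug discontinuation, and AESI. For AESI the section also plans a treatment difference in rates with a 95% confidence interval.

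Some AESI end treatment by rule. Protocol 5.4.1 lists "Malignancy, except for localized NMSC or carcinoma in situ of the cervix" among the reasons to stop study drug, and Protocol 5.4.1 and 6.1.7 require a permanent stop for gastrointestinal perforation and active TB.

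**The concern.** Groups 2 and 3 start their clock at Day 1, but membership depends on something learned 14 to 26 weeks later. A subject who dies or stops drug in that time is a non-switcher by definition. A switcher, by definition, was alive and on drug until the switch. The numerator for treatment-ending events is therefore close to the whole arm's, while the denominator comes from only part of the arm.

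Groups 1, 4 and 5 start at the switch, when membership is already settled, and are not inflated. If the hazard on a drug were the same for everyone, subjects randomised to it would still show higher rates of death and AE discontinuation in this table than subjects switched to it. A planned AESI rate difference between group 2 or 3 and group 1, 4 or 5 would carry the artefact. Group 2 against group 3 would be distorted too if the two arms switch at different rates.

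**Working it through.** The documents give no figure for this summary, so there is none to reproduce.

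**Inputs**
- Arm size: 600 upadacitinib, 300 adalimumab (SAP 4.2).
- Switch times: Weeks 14, 18, 22 and 26 (SAP 10.1.3). Mean time to switch t = 22 weeks is an assumption, varied from 14 to 26.
- Switch fraction s: not stated, so assumed 0.20 to 0.65. The upper end is 1 − 0.35, using the response rate planned for adalimumab in SAP 4.3. That is a rough proxy, because it is LDA by DAS28 (or ACR50) at Week 12 and the Week 26 switch uses CDAI. The lower end has no source.
- Follow-up of non-switchers T: 48 weeks, 96 weeks, and 48 weeks plus 5 years (about 309 weeks).

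**Formula.** Let E be the treatment-ending events on the first drug. Almost none can belong to a switcher.
- Rate per actual exposure to the original drug: E / (PY of non-switchers + PY of switchers before the switch)
- Rate under SAP 10.1.3: E / (PY of non-switchers)
- Ratio of the second to the first: 1 + s·t / ((1 − s)·T)

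**Results, t = 22 weeks**

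| s | T = 48 | T = 96 | T = 309 |
|---|---|---|---|
| 0.20 | 1.11 | 1.06 | 1.02 |
| 0.40 | 1.31 | 1.15 | 1.05 |
| 0.60 | 1.69 | 1.34 | 1.11 |
| 0.65 | 1.85 | 1.43 | 1.13 |

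With t between 14 and 26 weeks and T = 48, the ratio is 1.07 to 1.14 for s = 0.20, 1.19 to 1.36 for s = 0.40, 1.44 to 1.81 for s = 0.60, and 1.54 to 2.01 for s = 0.65.

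**Worked case:** N = 600, s = 0.40, T = 48, true rate 5.0 per 100 PY, 52.18 weeks per year.
- Non-switchers: 360 × 48 / 52.18 = 331.2 PY
- Switchers before the switch: 240 × 22 / 52.18 = 101.2 PY
- Events: 0.05 × (331.2 + 101.2) = 21.6
- Rate per actual exposure: 21.6 / 432.4 = 5.0 per 100 PY
- Rate under the SAP rule: 21.6 / 331.2 = 6.5 per 100 PY

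**Simulation check** (2,000,000 subjects per setting, constant hazard, switching independent of hazard). At 5 per 100 PY, 48 weeks and s = 0.40, the no-switch rate was 6.53, the original-drug rate 5.00 and the switched-group rate 5.05. With s = 0.60 and a mean switch at 23.4 weeks, the no-switch rate was 8.62 against 5.00. Switchers had no treatment-ending events on the first drug in any run. At 309 weeks the largest simulated ratio was 1.17 (s = 0.65, 10 per 100 PY), a little above the formula, mainly because events shorten the non-switchers' mean exposure.

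**The case against.** The strongest objection is that usable rates are already planned. The all-study-drug-exposure summary in SAP 10.1.3 keeps switchers' first-drug events and time, and the Week 26 analysis in SAP 10.1.2 censors at the switch. Neither has this defect, and no p-value rests on the affected table. A footnote pointing readers to those summaries might seem enough. This limits the point to one descriptive table. It does not cure that table: the all-exposure summary pools starters with switchers, so a reader cannot use it to correct groups 2 and 3, and a footnote leaves the AESI differences distorted.

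Three stronger readings are tempting, and the documents do not support them.
- A reader might infer that the long-term upadacitinib rates are biased throughout. They are not, because of the two analyses just named.
- A reader might infer that every rate in groups 2 and 3 is wrong. For AEs that do not end treatment, switchers' events and time are dropped together, so there is no mechanical inflation. AESI are affected only as far as they force a permanent stop: non-melanoma skin cancer and cervical carcinoma in situ are exempt (Protocol 6.1.7), and drug is not withheld for latent TB (Protocol 5.3.1.1). Even for treatment-ending events the numerator is not quite complete, since an AE that begins before the switch and causes a stop or death after it drops out.
- A reader might put follow-up at 26 weeks and quote an inflation of two-fold or more. The formula does give 1.21 to 2.57 there, but that needs every subject's follow-up to end at Week 26. SAP 4.4 places the unblinded analysis after all subjects have completed Week 26, so earlier enrolees will have more.

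It is also fair to object that adding switchers' first-drug data to groups 2 and 3 breaks the rule in SAP 10.3.3.2 that each subject counts in one group only. The fix has to respect or amend that rule.

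**Conclusion.** The concern holds for treatment-ending events in this one summary. The direction follows from the group definitions: the ratio exceeds 1 whenever anyone switches and any such event occurs on the first drug. It does not require a constant hazard. Only the comparison with groups 1, 4 and 5 uses the premise of equal hazards.

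The size rests on a switch fraction that the documents do not give. With 20% to 65% switching at a mean of 22 weeks, inflation is about 1.1 to 1.9 fold at 48 weeks of follow-up and about 1.02 to 1.13 fold at about 309 weeks. It matters most at early data cuts and fades with time. Because unaffected summaries exist, this should be corrected but does not undermine the safety analysis as a whole.

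**What to change.** **Preferred.** For event rates in this summary, start events and exposure for groups 2 and 3 at the Week 26 visit, among subjects still on their original drug. Membership is then settled before the clock starts, and each subject still counts in one group. Groups 1, 4 and 5 stay as they are. Data before Week 26 remain in the SAP 10.1.2 analysis and the all-exposure summary. The cost is SAP wording and changed cut dates, with no new data. The downside is that this table loses the early data of the no-switch groups.

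**Alternative.** Redefine groups 2 and 3 as all subjects who start the drug, from first dose and censored at the switch. In the worked case this restores 5.0 per 100 PY. It also requires amending the one-group rule in SAP 10.3.3.2 and the laboratory, liver and vital-sign tables that use the same groups (SAP 10.3.3.2, 10.3.3.3 and 10.4.3). The downside is that the groups are no longer never-switched subjects and that switchers appear in two groups.
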